- This study will continue for up to a maximum of 2 years (104 weeks) for each individual participant, or until esketamine nasal spray becomes accessible in the participant's local country, whichever occurs first. If esketamine nasal spray becomes accessible locally before the 2-year endpoint, then participants will be considered as having completed the open-label extension study and will have an end-of-study visit performed. Participants will be switched to a commercially available supply if in the opinion of the treating physician, the participant continues to benefit from treatment and the participant wishes to continue the esketamine nasal spray treatment.
- The dose of esketamine at the end-of-study visit (ie, esketamine becomes accessible locally) is not mandatory, this dose may be administered to allow time for transition to commercially available esketamine nasal spray. For subjects who receive a dose of esketamine nasal spray at the end-of-study visit, they will return for a safety follow-up visit 2 weeks after this visit.
- d For subjects who complete through end-of-study and do not administer a dose of esketamine nasal spray at this visit: 1) if participant's last dose was 2 weeks before this visit (ie, every 2 week dosing), then this visit is also considered the safety follow-up visit; or 2) if participant's last dose was 1 week before this visit (ie, once-weekly dosing), then the participant will return for the safety follow-up visit 1 week after this visit.
- e Participants who withdraw early from the study (ie, before Week 104/end-of-study) must have the early study withdrawal visit performed and then return for the safety follow-up visit 2 weeks after their last dose of esketamine nasal spray, unless they withdraw consent, are lost to follow-up, or have died. If the early study withdrawal visit is conducted on the same day as a scheduled visit, duplicate assessments are not required. If the early study withdrawal visit is performed 2 weeks or more after their last dose of esketamine nasal spray, this visit is also considered the safety follow-up visit.

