Selection of efficacy and safety evaluations

The full lists of efficacy and safety assessments for this study are described in Section 8, Study Evaluations.

The objective of this study is to collect long-term safety, tolerability, and efficacy information for esketamine nasal spray and to provide access to esketamine nasal spray for participants who successfully completed the 32-week maintenance phase of Study TRD3013 in countries where commercial esketamine nasal spray is not yet accessible.

Efficacy of esketamine nasal spray will be assessed as a secondary objective, and will be evaluated based on an assessment of relapse. The MADRS was chosen to assess efficacy as it is a well-known and widely accepted scale to assess the severity of depression. The relapse criteria used in this study are listed in Section 3.

At each study visit, adverse events will be assessed and investigators will evaluate the participant's mental status (including an assessment of suicidality). Clinical laboratory values, pregnancy testing, and body weight will be assessed at limited time points during the study, with additional assessments to be added at the discretion of the investigator. If clinically warranted, investigators may perform additional evaluations as needed during the study.

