- intracerebral hemorrhage.

43

- coronary artery disease following myocardial infarction, unstable angina, or revascularization procedure (eg. coronary angioplasty or bypass graft surgery).
- uncontrolled brady or tachyarrhythmias that lead to hemodynamic instability.
- hemodynamically significant valvular heart disease such as mitral regurgitation, aortic stenosis, or aortic regurgitation or heart failure (NYHA Class III-IV) of any etiology.
- significant pulmonary insufficiency, including chronic obstructive pulmonary disease.
- The investigator believes that for safety reasons or tolerability reasons (eg, adverse event), not expected to be resolved by dose and/or frequency adjustment, it is in the best interest of the participant to discontinue study intervention
- The investigator's opinion is that further continuation of study intervention would not be clinically justified
- The participant becomes pregnant
- Noncompliance with study drug administration defined as missing 3 consecutive doses

If a participant discontinues study intervention for any reason before the end of the open-label extension study, then the early study withdrawal and 2-week safety follow-up assessments should be obtained. Study intervention assigned to the participant who discontinued study intervention may not be assigned to another participant.

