Incidence of treatment-emergent AEs of special interest will be summarized, grouped in the following MedDRA-based categories: sedation, dissociation, suicidality, suggestive of abuse potential, cystitis and hepatic impairment. See Appendix 7 for a list of AEs in each category.

CONFIDENTIAL – FOIA Exemptions Apply in U.S.

A listing of participants who died will be provided.

Duration of TEAE

Additionally a bar chart will be created to present the duration of AEs (Treatment-emergent AEs in more than 5% of patients).

Duration of AEs will be calculated as:

- If AE start date = AE end date: AE end time AE start time
- If AE start date < AE end date: AE end date AE start date +1
- Note: for AE with outcome FATAL: AE end date= death date

AEs are categorized in following categories

- Duration: <= 1hour
- Duration: > 1 hour to <= 2 hours
- Duration: > 2 hours to <= 3 hours
- Duration: > 3 hours to <= 8 hours
- Duration: > 8 hours but AE start date=AE end date
- Unknown: Missing duration (ie. missing start or end time) and AE start date=AE end date
- Duration: 2 days to <= 7 days
- Duration: 8 days to <=28 days
- Duration: >28 days or AE ongoing

Bar chart that shows the percentage of AEs in each category is created.

Clinically significant weight change

- Calculate the number and % of patients with an increase of at least 7% in body weight at any point in time compared to baseline. Only include visits until last dose + 14 days.
- Calculate the number and % of patients with a decrease of at least 7% in body weight at any point in time compared to baseline. Only include visits until last dose + 14 days.
- Above proportions are calculated on all patients in the safety analysis set who have baseline and at least one post-baseline body weight measurement.
- If body weight missing, assume no 7% increase/decrease from baseline.

Medication

- Calculate the number and % of patients who received any concomitant therapy for TEAE. Denominator is patients in safety analysis set with at least one TEAE.
- Calculate the number and % of patients who received any concomitant therapy for TEAE, by preferred term. Denominator is patients in safety analysis set who developed the specific preferred term as TEAE.

• Analyses are based on data on AE page (AECONTRT). If AECONTRT is missing, assume no concomitant therapy received.

Days with AE

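### The 14-day cut-off and the missing-weight rule can drop the only scheduled extension weight yet keep the participant in the denominator, biasing the 7% weight-change proportions downward

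*SAP*

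**What the plan says.** SAP 5.3.2.1.1, under clinically significant weight change, counts participants with "an increase of at least 7% in body weight at any point in time compared to baseline", and likewise decreases of that size. Four features of the text matter:

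- Time limit: "Only include visits until last dose + 14 days".
- Denominator: "Above proportions are calculated on all patients in the safety analysis set who have baseline and at least one post-baseline body weight measurement".
- Missing data: "If body weight missing, assume no 7% increase/decrease from baseline".
- Data source: SAP 5.3 and 5.6 base the safety analyses on data from both TRD3013 and TRD4010, so parent-study weights appear to qualify as post-baseline.

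In the Schedule of Activities (Protocol 1.3), the body weight row has a single mark, under the combined Week 104/end-of-study/early withdrawal visit, with a window of ±3 days. Protocol 4.3 confirms the sparse schedule: "Clinical laboratory values, pregnancy testing, and body weight will be assessed at limited time points during the study", with anything further at the investigator's discretion.

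Two footnotes to the Schedule bear on timing. Footnote d covers participants who finish without a dose at the final visit, and treats that visit as the safety follow-up "if participant's last dose was 2 weeks before this visit (ie, every 2 week dosing)". Footnote e does the same for withdrawals: "If the early study withdrawal visit is performed 2 weeks or more after their last dose of esketamine nasal spray". It gives no upper limit on that gap.

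**The concern.** The cut-off sits on the day when the only scheduled extension weight is expected for one group, and before the day when it is expected for some early withdrawers. When that weight is excluded, no scheduled weight remains to show what happened during up to 104 further weeks of treatment. The participant is still likely to be in the denominator through a TRD3013 weight, and in effect counts as unchanged over the extension.

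This error can remove changers from the numerator but cannot add any, so it runs one way for both gain and loss. It is also tied to how participants leave the study, so it need not be random. The missing-weight rule acts in the same way on those never weighed in the extension, such as participants lost to follow-up. The primary objective is long-term safety, and this is the SAP's categorical weight result.

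**Working it through.** The plan gives no expected weight-change rate or sample size calculation to reproduce. The check has two parts.

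**Timing.** Inputs are the 14-day limit (SAP 5.3.2.1.1), the ±3-day windows on dosing and final visits (Protocol 1.3), the weekly or every-2-week dosing interval, and the discontinuation criterion in Protocol 7.1: "Noncompliance with study drug administration defined as missing 3 consecutive doses". The gap is the number of days from last dose to the scheduled weight. Where both visits move within their windows, the range is nominal ± (3 + 3) days.

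| Situation | Nominal gap | With both windows | Result under the cut |
|---|---|---|---|
| Dose given at the final visit | 0 | 0 | kept |
| Weekly, no dose at the final visit | 7 | 1 to 13 | kept |
| Every 2 weeks, no dose at the final visit | 14 | 8 to 20 | kept to day 14, dropped on days 15 to 20 |
| Withdrawal at the third missed weekly dose | 3 × 7 = 21 | 15 or more | dropped |
| Withdrawal at the third missed every-2-week dose | 3 × 14 = 42 | 36 or more | dropped |

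In the third row the final-visit window alone reaches 14 + 3 = 17 days. Even the narrower ±2-day safety follow-up window reaches day 16. No protocol deviation is needed to lose the weight.

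**Effect on the reported proportion.** Let

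- p = true proportion with a change of at least 7%;
- f = share of participants whose only extension weight is after day 14, taken as independent of weight change;
- g = share of changers already flagged by a TRD3013 weight.

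If affected participants stay in the denominator:

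reported = p × [1 − f(1 − g)], so the relative understatement is f(1 − g).

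The documents give none of p, f or g. For an assumed p of 10%:

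| f | g = 0 | g = 0.5 |
|---|---|---|
| 10% | 10 × (1 − 0.10) = 9.0% | 10 × (1 − 0.05) = 9.5% |
| 20% | 10 × (1 − 0.20) = 8.0% | 10 × (1 − 0.10) = 9.0% |

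At the planned 100 to 200 participants, f = 20% and g = 0 lose 2 of 10 changers (N = 100) or 4 of 20 (N = 200). Under the independence assumption, keeping the late weights returns the proportion to 10%.

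**Is it repaired elsewhere?** SAP 5.3.2.1.2 plans no sensitivity analysis. The extension-only outputs listed in 5.3.2.1.3 do not include weight.

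**The case against.** A 14-day limit matches the protocol's 2-week follow-up and is a defensible on-treatment choice. Weight is not a listed endpoint, and the study is descriptive with no hypothesis. Many participants are unaffected: those dosed at the final visit, those on weekly dosing who complete, and early withdrawers seen by day 14, which the usual sequence of withdrawal visit then follow-up would produce. These points stand. They limit the size of the problem but do not remove it.

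A reader might infer more than the documents support, in four ways:

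- **That every excluded weight is scored as no change.** The SAP does not call an out-of-window weight missing. The effect follows from reading its bullets together. A change of at least 7% on a TRD3013 weight still counts, because the endpoint is change at any time.
- **That the denominator is settled.** The SAP does not say whether it is formed before or after the cut, and the TRD3013 weight schedule is not in the documents. If it is formed after the cut, a participant with no other eligible weight leaves the table instead.
- **That long-term weight change is hidden from the report.** SAP 5.6.3.2 summarises weight and change from TRD3013 baseline at each time point with no 14-day limit stated, and Protocol 8.2 requires clinically relevant changes to be recorded as adverse events.
- **That about 43% of final weights are lost.** If both visits vary independently and uniformly over ±3 days, 21 of 49 combinations exceed day 14. That spread is assumed. The figure applies only to every-2-week participants not dosed at the final visit, whose number is unknown, and it is a share of weights, not the bias in the proportion.

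**Conclusion.** The point holds for the proportions with at least 7% gain or loss, and only for changes first seen at the final extension visit. Applied as written, the rules can discard a protocol-compliant weight while the participant normally stays in the denominator, so these proportions are biased downward. Late early withdrawals are the most exposed.

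The size cannot be fixed from the documents. The range of 8.0 to 9.5% against a true 10% rests on assumed values (f of 10 to 20%, g of 0 to 0.5), on independence between late weighing and weight change, and on a denominator that retains participants through TRD3013 weights. It also takes TRD3013 as the baseline, as SAP 5.6.3.2 does. If changers are more likely to be weighed late, the understatement is larger. If they are less likely, it is smaller. The correction should be made, but it concerns one descriptive safety table and not the study's main conclusions.

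**What to change.** Amend the weight-change bullets in SAP 5.3.2.1.1:

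1. Include the scheduled end-of-study or early withdrawal weight whatever its gap from last dose, and keep the 14-day on-treatment version as a sensitivity analysis.
2. Remove the missing-equals-no-change rule for the extension period.
3. Add an extension-only proportion with at least 7% gain or loss among participants with a TRD4010 weight.
4. State how many participants have no extension weight, and how many have one more than 14 days after last dose.

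Extending the cut to 30 days would not be enough. It would still drop a weight at the nominal 42-day gap. Nor is 30 days a settled window in the SAP: 5.3.2 and 5.3.2.1.3 use it for all adverse events, whereas 5.3.2.1.1 ends non-serious events at the 2-week follow-up and extends only serious ones to 30 days.

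The cost is SAP wording and one or two extra table rows, with no new data collection. The downsides are a smaller and somewhat selected denominator for the extension table, and some weights taken off treatment. The counts in item 4 let the reader judge the selection, and the sensitivity analysis shows what the late weights contribute.

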5.3.2.1.2. Sensitivity Analysis

Not applicable

5.3.2.1.3. Supplementary Analysis

Several supplementary analyses will be performed where a selection of AEs will be included

- Only including AEs starting at or after the initial administration of study intervention in Study 54135419TRD3013 and before the day of first dose in Study 54135419TRD4010
- Only including AEs starting at or after the initial administration of study intervention in Study 54135419TRD4010 through the day of last dose in Study 54135419TRD4010 plus 30 days. Following outputs will be repeated:
 - o Overall summary of TEAE
 - TEAE by SOC and PT
 - o TEAE by maximum severity
 - o TEAE by maximum relationship to esketamine

- o Treatment-emergent SAE
- o TEAE of special interest
- o TEAE leading to esketamine dose interruption or change
- o TEAE stratified by AE duration (end date same as start date versus end date later than start date)
- o Summary of days with TEAE
- o Proportion of TEAEs occurring on dosing days
- o Proportion of TEAEs which occur on dosing days with same day resolution
- Only including AEs starting at or after the initial administration of study intervention in Study 54135419TRD3013 through the day on which there is a switch of SSRI/SNRI or the day of last dose in Study 54135419TRD4010 plus 30 days, whichever comes first
- Only including AEs starting at or after the initial administration of study intervention in Study 54135419TRD4010 through the day on which there is a switch of SSRI/SNRI or the day of last dose in Study 54135419TRD4010 plus 30 days, whichever comes first

5.3.3. Estimand for C-SSRS

The C-SSRS is a low-burden measure of the spectrum of suicidal ideation and behavior that was developed to assess severity and track suicidal events through any intervention (Posner 2007). It is a clinical interview providing a summary of both suicidal ideation and behavior that can be administered during any evaluation or risk assessment to identify the level and type of suicidality present. The C-SSRS has been used frequently in clinical studies, and is a validated, standard measure for suicidal ideation assessment. Using the C-SSRS, the outcomes will be categorized using the scoring for the 11 categories:

Suicida	Suicidal Ideation (1-5)		
1	Wish to be dead		
2	Non-specific active suicidal thoughts		
3	Active suicidal ideation with any methods (not plan) without intent to act		
4	Active suicidal ideation with some intent to act, without specific plan		
5	Active suicidal ideation with specific plan and intent		
Suicida	al Behavior (6-10)		
6	Preparatory acts or behavior		
7	Aborted attempt		
8	Interrupted attempt		
9	Actual attempt		
10	Suicide		
Non-su	uicidal self-injurious behavior (11)		
11	Non-suicidal self-injurious behavior		

If no events qualify for a score of 1 to 10, a score of 0 will be assigned (0="no suicidal ideation or behavior that can be assessed on the basis of C-SSRS"). A participant with a score of 11 will be considered as not having suicidal ideation or behavior.

Composite endpoints based on the above categories are defined below:

- Suicidal ideation: A "yes" answer at any time during treatment to any one of the five suicidal ideation questions (Categories 1-5) on the C-SSRS.
- Suicidal behavior: A "yes" answer at any time during treatment to any one of the five suicidal behavior questions (Categories 6-10) on the C-SSRS.
- Suicidal ideation or behavior: A "yes" answer at any time during treatment to any one of the ten suicidal ideation and behavior questions (Categories 1-10) on the C-SSRS.

The following outcome is a numerical score derived from the C-SSRS categories. The score is created at each assessment for each patient.

• Suicidal ideation score: The maximum suicidal ideation category (1-5 on the C-SSRS) present at the assessment. Assign a score of 0 if no ideation is present.

Note that missing data should not be imputed.

Primary Trial Objective: To assess the long-term safety and tolerability of esketamine nasal spray in combination with an SSRI/SNRI in participants who have completed 32 weeks of esketamine nasal spray treatment in Study 54135419TRD3013.

Estimand Scientific Question of Interest: What is the safety and tolerability of esketamine nasal spray in combination with an SSRI/SNRI in participants who have completed 32 weeks of esketamine nasal spray treatment in Study 54135419TRD3013, based on the C-SSRS?

The estimand is defined by the following 5 components:

Study Intervention: esketamine nasal spray in combination with an SSRI/SNRI

Population: participants who have completed 32 weeks of esketamine nasal spray treatment in Study 54135419TRD3013

Variable: Number of participants who Shift from the baseline visit in Study 54135419TRD3013 to the maximum postbaseline C-SSRS score

Summary Measure: frequency distribution

Intercurrent events and their corresponding strategies:

	Name of Strategy for Addressing Intercurrent
Intercurrent Events	Events and Its Description
Discontinuation of (any component of) study	While on treatment: Only C-SSRS values up to
intervention for any reason	the date of the last dose will be used.
Withdrawal from the study	While on treatment: Same as above

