1.3. Schedule of Activities (SoA)

			Long-term I	Extension Phase		
		ESK Dosing:			Week 104/	
		Once Weekly			End-of-Study b,c,d/	
		or Every	Every	Every	Early Study	Safety follow-up
	Day 1 ^a	2 Weeks	4 Weeks	24 Weeks	Withdrawal Visite	visit ^f
Visit Window (Days)	+14	±3	±3	±3	±3	±2
Administrative Procedures						
Informed consent	Xg					
Inclusion/exclusion criteria	X					
Patient-reported outcomesh						
PHQ-9			X		X	
EQ-5D-5L			X		X	
Clinician-rated scales and questionnairesi						
MADRS: efficacy assessment			\mathbf{X}^{j}		X	
CGI-S			X		X	
C-SSRS (Since Last Visit version)			X		X	
Safety assessments						
Hematology/chemistry, urinalysis (local)k				X	X	X
Pregnancy testing ¹			X		X	X
Body weight					X	
Nasal examination predose ^m	X	X			X ⁿ	
Vital signs predose ^o	X	X			X ⁿ	
Vital signs postdose ^{o,p}	X	X			X ⁿ	
Vital signs ^{o,q}					Xr	X
Study intervention procedures						
Nasal treatment sessions ^{s,t}	X	X ^u			X ^c	
Drug accountability: esketamine	X	X			X ^c	
Medication compliance counseling (SSRI/SNRI) ^v	X	X				
Ongoing						
Concomitant therapy/psychotherapy	X	X			X	X
Adverse events	X	X			X	X

Abbreviations: C-SSRS=Columbia-Suicide Severity Rating Scale; CGI-S= Clinical Global Impression – Severity; eCRF=electronic case report form; EQ-5D-5L=European Quality of Life Group, 5 dimension, 5-level (questionnaire); MADRS=Montgomery-Asberg Depression Rating Scale; MDD=major depressive disorder; PHQ-9=Patient Health Questionnaire – 9; PRO=patient-reported outcome; SmPC=Summary of Product Characteristics; SNRI=serotonin-norepinephrine reuptake inhibitor; SSRI=selective serotonin reuptake inhibitor.

- Day 1 **should** be the same day as Week 32 visit from Study TRD3013. If a participant cannot receive the esketamine nasal spray dose on the same day as the Week 32 visit in Study TRD3013, the participant may be enrolled in this study (TRD4010) as long as they continue their current SSRI/SNRI and receive their first dose of esketamine nasal spray within 14 days of the Study TRD3013 Week 32 visit date; Day 1 of this study will be the day of the esketamine nasal spray dose. The sponsor will use the PROs, clinician-rated scales, and safety assessments, including clinical laboratory tests, from Week 32 in Study TRD3013 in the database for Day 1 in this study; these procedures do not need to be repeated for participants who return for esketamine nasal spray dosing within 14 days after the Week 32 visit in TRD3013.

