- The safety follow-up visit will be performed 2 weeks after the last nasal treatment session. For participants who withdraw early from the study, all safety follow-up visit assessments will be performed 2 weeks after their last dose of esketamine nasal spray unless they withdraw consent, are lost to follow-up, or have died. If the safety follow-up visit is conducted on the same day as a scheduled visit (eg, early withdrawal visit performed 2 weeks after last dose of esketamine nasal spray), duplicate assessments are not required.
- g Informed consent may be obtained from participants at any time in the 4 weeks before Day 1 (ie, at or after Week 28 visit in Study TRD3013).
- h Visit-specific PRO assessments should be conducted/completed before clinician-rated assessments, any tests, procedures, other consultations, or esketamine nasal spray administration to prevent influencing participant perceptions.
- Must be performed prior to esketamine dosing.

- In case of worsening of depressive symptoms and MADRS increase to >22, an additional assessment should be performed within the next 5 to 31 days to confirm the relapse criteria.
- Blood samples should be collected in fasting condition (at least 8 hours fasting, water is permitted). If clinically relevant abnormal results are found in hematology, chemistry, or urinalysis tests, tests should be repeated more frequently at the discretion of the investigator. Additionally, required laboratory tests as recommended in the respective SSRI/SNRI SmPC (or local equivalent, if applicable) should be performed. The investigator must record any clinically relevant changes occurring during the study in the Adverse Event section of the eCRF. Protocol-required safety laboratory assessments are listed in Appendix 8 (bicarbonate assay is optional, based on availability of the test at the local laboratory).
- Urine pregnancy testing (at site/local) for women of childbearing potential. Counseling on pregnancy prevention will be provided at all visits, if applicable. Additional serum or urine pregnancy tests may be performed, as determined necessary by the investigator or required by local regulation, to establish the absence of pregnancy at any time during the participation in the study.
- m Visual inspection of nostrils, nasal mucosa, and throat for nasal erythema, rhinorrhea, rhinitis, capillary/blood vessel disruption, and epistaxis.
- Only if participant receives a dose of esketamine at this visit (see footnote c).

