- O Vital signs: blood pressure, pulse/heart rate, respiratory rate.
- P Vital signs will be measured at approximately 40 minutes after esketamine nasal spray dose and subsequently as clinically warranted until blood pressure values decline. Participants must be monitored by a healthcare professional until the participant is considered clinically stable and ready to leave the study site. If blood pressure remains elevated for a prolonged period of time, assistance should promptly be sought from practitioners experienced in blood pressure management. Participants who experience symptoms of a hypertensive crisis should be referred immediately for emergency care.
- ^q At an early study withdrawal visit or the safety follow-up visit (no esketamine nasal spray dose), vital signs will be performed according to usual practice.
- Vital signs performed for participants not administrating esketamine nasal spray at this visit.
- If the participant has nasal congestion on the dosing day, a nasal decongestant can be used to reduce congestion (but not within 1 hour before esketamine dosing) or the dosing day can be delayed (per the permitted visit window).

- ^t Esketamine nasal spray dosing and related safety-monitoring procedures MUST be performed LAST at all visits. Esketamine nasal spray must NOT be administered before all other visit assessments are completed.
- ^u The frequency of nasal treatment sessions may be individualized on even week visits from once weekly to every 2 weeks based on severity of depressive symptoms and at the discretion of the investigator. If participants show early signs of worsening of depressive symptoms after reduced treatment frequency, the treatment frequency can be changed back to once weekly at any visit.

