5.3.2. Estimand for treatment-emergent adverse events

Primary Trial Objective: To assess the long-term safety and tolerability of esketamine nasal spray in combination with an SSRI/SNRI in participants who have completed 32 weeks of esketamine nasal spray treatment in Study 54135419TRD3013.

Estimand Scientific Question of Interest: What is the safety and tolerability of esketamine nasal spray in combination with an SSRI/SNRI in participants who have completed 32 weeks of esketamine nasal spray treatment in Study 54135419TRD3013, based on the development of treatment-emergent adverse events (AEs)?

The estimand is defined by the following 5 components:

Study Intervention: esketamine nasal spray in combination with an SSRI/SNRI

Population: participants who have completed 32 weeks of esketamine nasal spray treatment in Study 54135419TRD3013 and received at least one dose of esketamine in Study 54135419TRD4010

Variable: development of treatment-emergent AE: from the initial administration of study intervention in Study 54135419TRD3013 through the day of last dose in Study 54135419TRD4010 plus 30 days

Summary Measure: number and incidence of subjects who develop an treatment-emergent AE per person-time at risk

Intercurrent events and their corresponding strategies:

	Name of Strategy for Addressing Intercurrent
Intercurrent Events	Events and Its Description
	While on treatment: All AEs occurring through
intervention for any reason	the day of last dose plus 30 days are included in
	analysis
Withdrawal from the study	While on treatment: Same as above

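### If last dose means esketamine, the C-SSRS shift-to-maximum tables leave out an undosed early-withdrawal rating that can cover on-treatment days, and no supplementary analysis restores it

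*SAP*

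**What the plan says.** SAP 5.3.3 applies a while-on-treatment strategy to both discontinuation of any component of the intervention and withdrawal from the study. The rule is "While on treatment: Only C-SSRS values up to" "the date of the last dose will be used". No days are added, and the component is not named. The same estimand describes the intervention as esketamine with an SSRI/SNRI, whereas Protocol 2 uses the term study intervention for esketamine alone.

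The Schedule of Activities (Protocol 1.3) lists "C-SSRS (Since Last Visit version)" every 4 weeks and at the shared Week 104/end-of-study/early-withdrawal visit, but not at safety follow-up. A footnote on the clinician-rated scales says "Must be performed prior to esketamine dosing". The vital-signs footnote speaks of "At an early study withdrawal visit or the safety follow-up visit (no esketamine nasal spray dose)".

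SAP 5.3.3.1.1 plans three shift summaries from the TRD3013 baseline. Two go to the postbaseline maximum (score and category). The third, for the ideation score, goes to the maximum during treatment. SAP 5.3.3.1.2 (sensitivity) and 5.3.3.1.3 (supplementary) are both marked not applicable.

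Two other safety analyses in the SAP reach past the last dose. For adverse events, those through "the day of last dose plus 30 days are included in" the analysis (SAP 5.3.2). For weight change, SAP 5.3.2.1.1 says "Only include visits until last dose + 14 days".

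**The concern.** A look-back form is dated at the visit but describes the interval before it. A cut-off on the rating date can therefore discard information about days on treatment. For someone who stops between four-weekly ratings, the next scheduled C-SSRS is the early-withdrawal rating. If no esketamine is given that day, the rating falls after the cut-off.

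The variable is a maximum, so the loss runs one way: it can lower the recorded score or leave it unchanged. It may also not be random, because Protocol 8.2.5 names signs of suicidal ideation or behavior as a reason to consider discontinuing. Any bias is then toward the category with no ideation or behavior. SAP 5.3.1 names the C-SSRS as one of two primary endpoints.

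The SAP gives no reason for a narrower window here than for adverse events, which carry the same while-on-treatment label. In this study weight is scheduled only at the same final visit, and the 14-day weight rule keeps many of the visits that the C-SSRS rule drops.

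**Working it through.** The documents give no figure to reproduce. The check has three parts.

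**1. Which final ratings are kept.** The rule keeps a rating if its date is on or before the last dose.

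- Final visit on a dosed day: the C-SSRS is done before dosing on the same date, so it is kept. The schedule also allows an early-withdrawal visit to coincide with a scheduled one: "If the early study withdrawal visit is conducted on the same day as a scheduled visit, duplicate assessments are not required".
- Undosed early-withdrawal visit, last dose read as esketamine: dropped.
- Undosed early-withdrawal visit, last dose read as either component and the SSRI/SNRI still taken: kept.
- Undosed end-of-study visit: unclear. Local access to esketamine is a withdrawal reason in Protocol 7.2 but counts as completion in Protocol 4.4 and SAP 5.2, and the cut-off is written only for discontinuation and withdrawal.

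The esketamine reading has support. Besides Protocol 2, SAP 4 defines the Safety/Efficacy set by esketamine dosing and SAP 5.1.1 sets Study Day 1 by it.

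**2. Treatment days covered by a dropped rating.** Inputs from Protocol 1.3: C-SSRS every 28 days, dosing every 7 or 14 days. Assumptions: nominal dates; previous C-SSRS on a dosed visit (day 0); look-back running from that C-SSRS; undosed withdrawal visit on the next dosing date; no extra ratings.

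| Dosing | Last dose (day) | Undosed visit (day) | Treatment days covered | Look-back (days) |
|---|---|---|---|---|
| Weekly | 0 | 7 | 0 | 7 |
| Weekly | 7 | 14 | 7 | 14 |
| Weekly | 14 | 21 | 14 | 21 |
| Weekly | 21 | 28 | 21 | 28 |
| Every 2 weeks | 0 | 14 | 0 | 14 |
| Every 2 weeks | 14 | 28 | 14 | 28 |

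If stopping is equally likely after any dose in the cycle:

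- Weekly: (0+7+14+21)/4 = 10.5 treatment days in a mean look-back of (7+14+21+28)/4 = 17.5 days; 42/70 = 60%.
- Every 2 weeks: (0+14)/2 = 7 treatment days in a mean look-back of (14+28)/2 = 21 days; 14/42 = 33%.

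At 1 of 4 stopping points (weekly) or 1 of 2 (every 2 weeks), no treatment day is lost.

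**3. Effect on the table.** The documents give neither an early-withdrawal rate nor a rate of positive ratings first seen at an undosed final visit, so the bias cannot be computed. Expected enrolment is 100 to 200 (SAP 3). One participant placed in too low a category moves a percentage by 1/100 = 1.0 point or 1/200 = 0.5 point.

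**The case against.** The strongest reply is that Protocol 9.4.2 asks for C-SSRS summaries during treatment, and SAP 5.3.3 simply implements that. A rating after the last dose mixes on- and off-treatment time and, unlike an adverse event with an onset date, cannot be split. This stands as a reason not to insist on a wider primary window. It does not answer the loss of treatment days that the discarded rating also covers.

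Several limits on the effect also stand:

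- Protocol 8.2.5 calls for more frequent C-SSRS ratings, at the investigator's discretion, if early signs of ideation appear. Those dated by the last dose count.
- Protocol 4.3 has mental status, including suicidality, evaluated at each visit.
- A participant with an equal or higher earlier postbaseline score, including one from TRD3013 (SAP 5.3), is unaffected.
- Suicidality adverse events, the MADRS suicidal-thoughts item and relapse narratives are reported separately. The by-time-point C-SSRS table does not repeat the cut-off and, with the visit mapping in SAP 5.1.1, may show the rating.

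These limit concealment, but none of them corrects the shift table.

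A reader might infer that every early-withdrawal rating is lost. The documents do not support that: dosed-day ratings are kept, last dose is undefined, two of the three shift summaries carry no cut-off of their own, and the parenthesis in the vital-signs footnote may refer only to safety follow-up. A reader might also take 60% and 33% as chances of a missed maximum. They are shares of calendar days.

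Nor does the SAP establish last dose plus 30 days as the window to copy. SAP 5.3.2 uses it, but SAP 5.3.2.1.1 ends treatment emergence at the 2-week follow-up visit and extends only serious events to 30 days.

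**Conclusion.** The concern holds conditionally. If last dose means esketamine, which is the better supported reading but is not stated in SAP 5.3.3, the while-on-treatment rule excludes an undosed early-withdrawal rating from the shift-to-maximum analysis. It does the same to an undosed end-of-study rating if the cut-off applies to those participants. The excluded rating can be the only scheduled one for 0 to 21 treatment days (weekly dosing) or for 0 or 14 (every 2 weeks). Any effect on the maximum is downward, and its size is unknown. The day counts rest on nominal dates, a look-back from the previous C-SSRS and no discretionary ratings in between.

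Two wording faults hold on any reading: last dose is undefined for a two-component intervention, and the shift summaries in SAP 5.3.3.1.1 do not share one end point.

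A reader might go further and conclude that the plan hides suicidality at withdrawal or that its estimand is invalid. The documents do not support either, given the separate suicidality outputs and the protocol's own restriction to treatment. This is a cheap improvement to a single-arm descriptive study, and worth making.

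**What to change.** In SAP 5.3.3, state that last dose is the last esketamine dose and that the rule applies alike to discontinuations, withdrawals (including those due to local access) and undosed completers. Use that definition for the during-treatment wording of the composite endpoints in 5.3.3 and for all three shift summaries in 5.3.3.1.1.

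In 5.3.3.1.3, replace the not-applicable entry with a shift-to-maximum table on all postbaseline C-SSRS ratings, including the first rating after the last dose at the early-withdrawal or end-of-study visit. List the ratings dated after the last dose with a flag.

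The sponsor could instead make this the primary table and keep the up-to-last-dose version as the sensitivity analysis, recorded in SAP Appendix 2 because Protocol 9.4.2 refers to treatment. If a day window is preferred, SAP 5.3.2 and 5.3.2.1.1 must first be reconciled. With the ±3-day visit window, an every-2-week visit at 14 days spans 11 to 17 days after the last dose, so a 14-day limit would lose late ones. After two missed doses the visit spans 25 to 31 days, and after three 39 to 45, so a 30-day limit would lose some or all of these. Using all ratings avoids the choice.

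The cost is a few SAP sentences, one table and one listing on data already collected. The drawback is that some off-treatment time enters the added table, typically 7 days (weekly) or 14 days (every 2 weeks), and the look-back form cannot separate it. Showing both tables makes that visible.
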